### **Cascade indicators:**

We will gather quantitative information from existing patient records (retrospectively) regarding the current functioning of contact investigation and LTBI management in all intervention health facilities in all countries.

Whose records are reviewed: Our objective is to collect data on 100 to 150 household contacts identified at each participating site. This is the expected number of contacts for approximately 30-35 index cases (may be more for Canadian sites). This data collection will start with consecutive patients, or a representative sample across the observation period, diagnosed with confirmed active Pulmonary TB during an interval ending 6 months ago. This interval is selected so that all screening and diagnostic procedures will have been completed by the time of review, yet is recent enough that problems identified in questionnaires and interviews are likely to accurately reflect the current situation.

Information to be gathered: Key information to extract will include the following: 1) The number of patients diagnosed with microbiologically confirmed active Pulmonary TB (index cases), 2) The number of their household contacts who are identified as eligible for symptom screening and LTBI testing, 3) The number who are questioned about symptoms only, and the number who complete LTBI testing procedures - using Tuberculin Skin Test (TST) or Interferon Gamma Release Assays (IGRA), 4) The number who are LTBI test positive, 5) The number of contacts with positive LTBI tests who have a medical evaluation to exclude active TB (e.g. medical examination, chest X-ray and sputum test if applicable), 6) The number of contacts with positive LTBI tests who complete medical evaluation and start LTBI therapy. The number of household contacts of index cases and the identification, investigation and treatment of household contacts of index cases will be abstracted from different sources. Sources may include the index case registry, treatment cards and other sources described below.

A standardized form will be used to record this information.

Sources of information: In most clinics in DOTS programs (the acronym for the WHO recommended approach to diagnosis, treatment and follow-up of patients with active TB), all patients with newly diagnosed PTB are registered in the TB Patient Treatment Registry (In Brazil – this is the "Green Book"). Their identified close/household contacts may be listed on the DOTS treatment cards of their index cases (in most DOTS programs). The investigation and management of these contacts may be summarized on the same treatment cards, or in the medical records of these same patients. In a few programmes this will be summarized in Latent TB registries, or Contact registries, but in most sites this information will be gathered from several sources.

**Interviewer administered Questionnaires:** At the same time we will gather information about the problems and barriers that impede TB contact management. These will be mapped onto the Cascade of care in Latent TB.

Who is interviewed: At each Intervention health facility, 5 groups of persons are to be interviewed: 1) Patients with active PTB (Index cases); 2) Household contacts who did come to be seen at the clinics; 3)

Household contacts who did not come to clinics; 4) Community health workers; 5) Nurses and doctors. Of the household contacts interviewed, an equal number should be adults in families with, and without children. Of the doctors and nurses the priority is to select those most directly involved in the care of patients with active PTB, and their contacts.

How many will be interviewed: In Vietnam and Indonesia, the aim will be to interview up to 5 persons in each of these categories at each site - giving a minimum of 40 persons in each group. In countries with fewer health facilities, such as Ghana, Benin and Canada - then the number in each group will be increased to 20 per site. This will result in a total of 40 interviewees in each group in Ghana and Benin, and 80 per group in Canada. In many health facilities the number of health workers, especially physicians and nurses, who work in the TB programme, is less than 5, and in Benin, Ghana and Canada - will certainly be less than 20. In all intervention health facilities we will interview all TB nurses and doctors - up to a maximum of 5 each (for Vietnam and Indonesia), and 20 each in the remaining countries

Questionnaires: Three questionnaires will be used:

Health workers: This will investigate their knowledge and attitudes regarding contact management, diagnosis and treatment for LTBI, as well as knowledge and attitudes about TB diagnosis and treatment.

Index cases: This will investigate TB patients' knowledge, attitudes and perceptions about TB and transmission, as well as their health system experiences.

Contacts: This will investigate household contacts' knowledge, attitudes and perceptions regarding TB and transmission, and their health system experiences with contact investigation.

These questionnaires are attached in the Appendix. These were originally developed and used in an earlier study in Bandung, then revised and used in a pilot study in Brazil. These have been revised again based on this experience, and further revised based on pre-testing in Montreal. Certain questions are site-specific; these will be adapted to the local situation. All questionnaires will be pre-tested for understanding and adequacy of responses in each country, then revised for final versions. These final versions will be translated into local languages as needed.

Questionnaire administration: All questionnaires will be administered by trained interviewers. The interviewers will explain each section, reading the script printed in the questionnaires at the start of each section. For some questions they read all responses and ask for a single response, and others are open-ended. For some of these open questions the most common responses are listed, allowing the interviewer to simply tick if these responses are given. Other responses will be written down as free text.

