**Calgary:** In Calgary, all patients newly diagnosed with active PTB are assigned a public health nurse who is based at the Calgary Public Health TB Clinic. This nurse interviews the family in the clinic, or if this cannot be arranged, the nurse will make a home visit. Identified contacts that do not come to clinic are contacted via telephone twice and if unsuccessful, a letter is sent on two occasions. Contacts that live in the city of Calgary are referred to the Foothills hospital TB clinic for evaluation. If they do not come the public health nurse will call them twice. If LTBI is diagnosed, LTBI therapy is individualized. Individuals who drop out during LTBI therapy are called by clinic staff.

**Benin:** The Benin NTP policy is to ask all newly diagnosed active pulmonary TB cases to bring all children aged under 5 living in the same household to the nearest TB treatment facility for evaluation. The patient is also asked to advise all symptomatic household contacts to visit diagnostic centres for evaluation. Home visits are not done to identify or screen contacts. The adult and pediatric 4RIF vs 9INH trials are being conducted at the Centre National de Pneumo-Phthisiologie (CNPP) in Cotonou. The randomization units for the proposed trial will be two independently staffed treatment centres in Cotonou – the CNPP, and the Centre de Akron a Portonovo.

**Ghana:** In Kumasi, Ghana, all patients newly diagnosed with active pulmonary TB are interviewed, and screened for symptoms of active PTB. Contacts that do not have symptoms are not assessed further except for children under the age of 5 and known HIV infected persons – who are referred to the hospital TB clinic, where they receive 6 months INH. Individuals who drop out during LTBI therapy are contacted by telephone.

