**Indonesia:** In Indonesia, the National TB Programme (NTP) has recognized the high risk of disease in contacts and adopted symptom screening of contacts, but this is rarely implemented, and is not recorded nor reported. Bandung city in West Java, Indonesia has a population of approximately 2.5 million. The greater Bandung area, however, has a population of over 7 million. The incidence of new smear positive TB is approximately 100 per 100,000 population for a total case load of approximately 2000 new cases each year. Both the city and the area is served by a network of community based primary care clinics. The adult and pediatric trials comparing 4RIF and 9INH recruited patients from community clinics in the central Bandung area, in conjunction with a clinic at the University of Padjadjaran. We propose to conduct the study in 8 of these community clinics - where the current LTBI trial was well received, and well executed.

**Vietnam:** At the Vietnam site, household contacts are identified by clinical officers working at District Tuberculosis Units (DTU). The clinical officers interview newly diagnosed patients with active TB, and make a list of household contacts that are eligible for screening. These contacts attend the DTU for clinical assessment and chest X-ray. TST is not routinely performed. Despite national policies recommending 6INH for contacts who are children or with known HIV infection, few are treated.

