### **Data analysis;**

The number of household contacts **expected** will be calculated as the number of index cases times the average number of household contacts identified in the same countries, or countries with similar resource levels (based on World Bank classification of national income level), from two recent systematic reviews (Fox and Morrison). This will be compared to the number actually identified.

We will match the problems identified with each step in the Cascade associated with more than 10% losses/drop-outs, based on the Indicator review. For example if a large number of identified contacts are not initially screened (in the systematic review, we found that 30% of identified contacts were lost at this stage), then we will identify problems associated with that step in the Cascade and prioritize identifying interventions to address these (See Figure 3 for schematic). The problems to be addressed may have been identified from questionnaires completed by patients with active TB, their contacts, or the health care

providers. Simple proportions will be estimated at each centre, corrected for clustering at the household level via generalized estimating equations.

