**Reporting:**

The Contact Management registries will be used to generate quarterly reports of diagnoses of contacts, and cohort reports of treatment outcomes in TST positive contacts. These quarterly reports will be modeled after the quarterly reports of case finding, and treatment outcomes that are recommended by WHO , and used by the National TB control programmes in almost all LMIC.

The quarterly reports will be based on data abstracted from the Registries (they are designed to be abstracted very easily), and initially prepared by study staff. These reports will include the number of new pulmonary TB patients, household contacts identified, investigated with symptom screening and TST, had TST reading, TST positive who underwent medical evaluation, and initiated LTBI medication.

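### The cascade counts medical evaluation and treatment start only in test-positive contacts, which does not fit sites that evaluate or treat contacts without a test

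*Protocol*

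**What the plan says.** *Cascade indicators* (Data Gathering) lists six counts to be taken retrospectively at intervention facilities. Item 3 separates two groups: "The number who are questioned about symptoms only, and the number who complete LTBI testing procedures". Item 5 is "The number of contacts with positive LTBI tests who have a medical evaluation to exclude active TB" and item 6 is "The number of contacts with positive LTBI tests who complete medical evaluation and start LTBI therapy". No later item follows up the contacts who had symptom questions only.

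*Reporting* (Phase 2 Enhanced Reporting) provides for "cohort reports of treatment outcomes in TST positive contacts". Its list of quarterly counts ends with "TST positive who underwent medical evaluation, and initiated LTBI medication".

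*Specific Sites* describes practice before the trial. For Vietnam, contacts have a clinical assessment and chest X-ray at the district unit, and "TST is not routinely performed. Despite national policies recommending 6INH for contacts who are children or with known HIV infection, few are treated". For Ghana, children under 5 and known HIV-infected contacts are the ones "who are referred to the hospital TB clinic, where they receive 6 months INH"; no test is mentioned.

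Elsewhere starts carry no test condition. *Study design* lists started on treatment as a cascade indicator. *Study Outcomes* counts household contacts who started therapy. *Data Analysis for Phase 2* takes the proportion of identified contacts who start as the primary outcome.

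**The concern.** The cascade is the measurement on which the intervention is built. *Data analysis* for Phase 1 matches problems to "each step in the Cascade associated with more than 10% losses/drop-outs". *Selecting the Solutions for Phase 2* feeds the site's cascade data into the simulation model that compares the cost and effect of candidate solutions. The cross-over study reuses the cascade unchanged.

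If a contact can be evaluated or treated at a site without a test, but the last two items admit only test-positive contacts, that contact is recorded as lost at testing. Evaluations and starts are then understated in the cascade and in the model inputs. The loss among untested contacts whom local policy already makes eligible, which is the gap the Vietnam description points to, has no indicator. A start would also mean one thing in the cascade and another in the trial outcome.

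**Working it through.** **Setting the sections side by side**

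| Place in the protocol | Who counts as evaluated or started |
|---|---|
| *Study design* | Contacts started on treatment, no test condition |
| *Cascade indicators*, items 5 and 6 | Positive LTBI test required |
| *Study Outcomes*; *Data Analysis for Phase 2* | Any household contact who starts |
| *Reporting*, outcome cohorts | Skin-test-positive contacts only |
| *Reporting*, count of those initiating medication | Can be read either way |
| *Specific Sites*, Vietnam | Assessment and X-ray without routine test (stated) |
| *Specific Sites*, Ghana | INH with no test mentioned (inferred) |

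Item 5 gives medical examination and chest X-ray as examples of evaluation. That is what Vietnam does routinely, yet item 5 excludes it because no positive test came first.

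**Sites concerned.** From Table 1, Ghana and Vietnam have 2 + 8 = 10 of 24 randomization units and 1,900 + 1,900 = 3,800 of 10,425 expected contacts (36.5%). The main-study cascade is taken only at the intervention facilities among them.

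**Cascade sample per site.** The protocol expects 100 to 150 contacts from about 30 to 35 index cases. At its 4.2 contacts per case, 30 × 4.2 = 126 and 35 × 4.2 = 147. Both lie in the stated range, so that figure reproduces.

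**Understatement of starts.** The sample-size section assumes that 10% of contacts start at baseline. Let f be the share of those starts made without a test. The protocol does not give f, so it is varied over its full range.

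- True starts = 0.10 × contacts
- Recorded by item 6 = 0.10 × contacts × (1 − f)
- Treated contacts shown as lost at testing = 10 × f percentage points of identified contacts

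| f | Item 6, 126 contacts (true 12.6) | Item 6, 147 contacts (true 14.7) | Shown as lost at testing |
|---|---|---|---|
| 0 | 12.6 | 14.7 | 0 points |
| 0.25 | 9.5 | 11.0 | 2.5 points |
| 0.50 | 6.3 | 7.4 | 5 points |
| 0.75 | 3.2 | 3.7 | 7.5 points |
| 1 | 0 | 0 | 10 points |

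This range covers starts only. The protocol gives no figure from which to bound the missing evaluations in item 5.

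**Effect on the 10% rule.** Take an assumed clinic with 100 contacts and no testing, where 12 contacts are eligible under policy and 8 of them start. The literal cascade shows 100/100 = 100% loss at testing. With the 8 moved to their own branch, the loss is 92/100 = 92%. Both far exceed 10%, so testing is flagged either way. What the literal cascade does not show is the loss among the eligible, here 4/12 = 33%.

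**The case against.** The best case for leaving the text alone is that the six items are introduced as included information rather than as a complete list. The sentence after them speaks of abstracting the treatment of household contacts without a test condition. The cross-over section refers to seven cascade steps, and the form itself is not shown. A sensible abstractor might therefore record untested starts anyway. That is possible, but the only written rule for items 5 and 6 says otherwise.

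Several stronger readings are tempting, and the protocol does not support them:

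- *Baseline starts vanish and loss at testing is total.* That is the extreme f = 1 with no testing at all. In Vietnam few contacts are treated, so few starts can be missed. Ghana's untested route is inferred from silence. The Benin and Indonesia descriptions do not state treatment without a test.
- *The wrong step is chosen for action.* The testing step exceeds the 10% trigger under either count. Contacts of all ages are eligible, so that loss is largely real. Questionnaires and the site narrative also inform the choice of solutions.
- *The planned check of registry starts against the other sources must disagree by definition.* *Contact Management Registries* ties the positive-test condition to X-ray and medical evaluation. Treatment initiation is recorded as a separate item for identified contacts.
- *Quarterly start counts exclude untested contacts.* That wording is ambiguous. Only the outcome cohorts are clearly restricted.
- *The primary outcome is biased.* As defined, it has no test condition. *Ascertainment of study outcomes* takes starts from clinic or hospital records on a standard form at all sites.

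One part of the last point stays open. *Time-table of Phase 2* says the analysis will use counts from the quarterly reports. If so, and if the ambiguous item is read narrowly, the restriction would reach the trial outcome.

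**Conclusion.** The point holds as a mismatch of definitions. A stated counting rule does not fit practice described at the protocol's own sites and conflicts with the protocol's own unconditional counts of starts. It is established by the text for Vietnam and by inference for Ghana. It affects the cascade, the model inputs drawn from it and the treatment-outcome cohort reports.

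For starts the size is between 0 and 10 percentage points of identified contacts. This assumes the protocol's 10% baseline and an untested share that the protocol does not give; in Vietnam it is probably near the low end. For evaluations the size cannot be estimated. The main practical loss is that drop-out among untested, policy-eligible contacts is not visible. The primary outcome as defined stands, subject to settling whether the quarterly reports are its source. The change is worth making because it is cheap, not because it threatens the trial's main comparison.

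**What to change.** 1. In *Cascade indicators*, redefine items 5 and 6 as all household contacts medically evaluated and all who start LTBI therapy, each split into positive test and no positive test.
2. In *Reporting*, give starts and treatment outcomes for all contacts started, with the same split, and reword the ambiguous item.
3. Use the all-contact counts as inputs to the simulation model.
4. Report the untested branch descriptively. Do not apply a separate 10% loss rule to it: with about 12 contacts, as in the illustration, one loss is 8% (1/12) and two are 17% (2/12), so the rule would turn on one contact.
5. Reconcile *Study design*, *Study Outcomes*, *Ascertainment of study outcomes*, *Cascade indicators*, *Reporting* and *Time-table of Phase 2*, so that a start has one meaning and the primary outcome has one named source.

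The cost is a few extra counts on the cascade form and the quarterly report, taken from records already being abstracted. Only recording changes; no testing or treatment rule is proposed.

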### **Measuring Costs:**

At each participating site, we will estimate costs, from the perspective of the health system, particularly the TB programme, of the following three major activities:

1. *TB related health care activities* including contact investigation, and diagnosis and treatment of active and latent TB. To estimate these health system expenditures at the participating sites, we will use bottom up micro-costing methods. This means that, as much as possible, we will directly measure resources used and staff time for each specific TB related activity, at each site. Staff time will be measured using Time And Motion (TAM) measurement where all clinical staff involved in TB related activities will be shadowed for a complete work day. The amount of time spent on active TB vs. LTBI will be carefully quantified. The research staff who will shadow the clinical staff will record stop and start times for each type of clinical activity (eg., clinical encounter, administrative activity, training etc) and type patient (eg active TB, LTBI or non TB). Research staff will be trained to ensure that they do not interfere with the work performed by clinical staff being shadowed and to ensure that they

respect the privacy of the staff being observed as well as the patient. The research staff will remain outside the consultation room at all times so that patient confidentiality is not compromised. A script describing what the TAM measurements are and how they will be done will be read to the health care worker by the research staff before the exercise begins. Measurements will be conducted at 3 different times in Intervention facilities and twice in control facilities.

Costs associated with building facilities will be tabulated using a questionnaire and apportioned based on staff/space allocations for the TB program. Other resources such as consumables and overhead will also be quantified. These costs will be quantified twice –at the start of Phase 1 (before any study-related interventions), and near the end of Phase 2 after full implementation of contact investigation and LTBI management.

2. *The public health intervention* itself - including research costs and costs for health care staff and administrators to participate in the research. Research costs will include time of research staff and investigators in Phase 1 and Phase 2. In Phase 1 this will include , data extraction for cascade indicators, measurement of outcomes, conducting interviews, measuring costs, data analysis and assistance in the selection of appropriate solutions. In Phase 2 this will include initial and in-service training of health care staff at participating sites (and retraining as needed for staff turnover) for LTBI diagnosis and management, implementation of full contact registry, implementation and training for solutions following identification of problems. This information will be useful to understand the “learning curve” at the clinics – how long does it take to get the contact investigations running well, with few missed cases, complete Contact Registries, and resolution of all administrative problems. How much time is required for monitoring and supervision? How frequent do in-service training visits need to be? To measure the time spent by research staff on ACT4 trial activities, time and motion self report activity logs will be completed monthly by all research staff involved in ACT4 throughout the study. For staff time, all activities will also be tabulated for health care personnel who contribute time in the research study, including meetings, interviews and training sessions. Logs specifying time spent on different research activities will be submitted to the central coordinating centre who will calculate the total amount of time spent on each discrete activity.

3. *The costs of the solutions* - A fixed amount of money will be given to sites for solutions (See page 18 for more detail). Sites will be asked to provide a detailed breakdown of how funds allocated for solutions were spent as well as details of any additional human resource requirements while solutions were in place.

